### **2.4 Rationale for studying lenalidomide as maintenance therapy in AML.**

Therapy for maintaining longer-term remissions after consolidation therapy in AML patients with high-risk disease is a critical need. Unlike the treatment protocols for ALL, there is no current standard for maintenance therapy in AML. Previous attempts at maintenance therapy in AML, utilizing redundant chemotherapy-based protocols have been met with minimal success. We therefore propose a clinical trial evaluating low intensity, continuous dosing of lenalidomide in patients with high risk AML who have responded to induction/consolidation chemotherapy and are not immediately candidates for BMT. From our own data, the expected relapse free survival in this cohort of younger patients with higher risk disease who do not proceed for stem cell transplant is 8.5 months. Approximately 25% of these patients may become eligible for and proceed to transplant, but the majority are left without meaningful therapy until relapse.

Based on published data, NK cells are important mediators of immune surveillance, particularly in AML. In addition to affecting direct cytotoxicity of AML blasts, NK cells may also alter the cytokine and immune cell (eg. T-lymphocytes) milieu to favor anti-leukemia immunity. Lenalidomide has been shown to enhance NK cell activity and numbers – making it an important agent to study in a setting of low disease burden (ie. minimal residual disease after chemotherapy). As part of the clinical trial, we also aim to study the effects of lenalidomide on NK cell activity – both at baseline (prior to lenalidomide treatment) and at several time points during treatment. This will help us derive more insight into the actions of lenalidomide on NK cell activity and how it relates to maintenance of remission in patients with AML.

The rationale for the selected dosing of lenalidomide maintenance is drawn from previous experience in chronic dosing of lenalidomide for maintenance strategy. In the AML experience described above, Fehniger, et. al. treated patients in the maintenance phase with 10 mg orally

daily. In multiple myeloma maintenance studies, lenalidomide was dosed at 10 – 15 mg orally daily, continuously. These doses have therefore been shown to be safe and active in a long-term dosing strategy.

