#### 4.1 Treatment Schema

##### 4.1.1 Maintenance Lenalidomide Dosing:

Lenalidomide continuous dosing on days 1- 28 of a 28 day cycle.

Dose of lenalidomide is as follows:

- Starting dose (DOSE LEVEL 0): 10mg orally daily during cycle 1
- If after one cycle, the patient has persistent evidence of (1) minimal residual disease or (2) morphologically active disease AND is tolerating their starting dose of lenalidomide, their dose may be increased to the next higher dose level for the remainder of the study. A maximum of 2 dose escalations per patient are allowed if well tolerated.

Table 1. Dose escalation and de-escalation table.

Dose Level	Lenalidomide Dosing
-2	5 mg PO Every other Day
-1	5 mg PO Daily
0 (Starting dose level)	10 mg PO Daily
1	15 mg PO Daily
2	20 mg PO Daily

One cycle of therapy is considered 28 days. Therapy will be continuous; interruptions and dose-adjustments for toxicity will be implemented as needed.

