## 6.0 DOSING DELAYS / DOSE MODIFICATIONS FOR SUBSEQUENT CYCLES

### 6.1 Dose levels for dose adjustments Table 1

Dose Level	Lenalidomide Dosing
-2	5 mg PO Every other Day
-1	5 mg PO Daily
0 (Starting dose level)	10 mg PO Daily
1	15 mg PO Daily
2	20 mg PO Daily

6.1.1. Dose levels different than dose described may be allowed after discussion with the PI.

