Scenario	True Median (months)	Pr(Stopped Early)	Mean No. patients	Average Trial Duration (months)
1	4	0.968	18.9	21.5
2	6	0.410	37.7	30.6
3	8	0.102	46.4	34.8
4	10.5	0.030	48.9	36.0

5	12	0.017	49.3	36.2
---	----	-------	------	------

For the primary analysis of the efficacy endpoint, we will compute the Bayesian posterior probability of  $\text{Pr}(\lambda_E > \lambda_H + \delta | \text{data})$ . As a secondary analysis, we will perform a competing risk analysis treating stem cell transplant as a competing event for RFS.

In addition, we will continuously monitor treatment-related toxicities using the Bayesian approach of Thall, Simon, Estey (1995). Specifically, the trial will be stopped if  $\text{Prob}(\pi T > 0.30 | \text{data}) > 0.92$ , where  $\pi T$  is the toxicity rate and we assume a beta (0.6, 1.4) prior for  $\pi T$ . That is, if at any given time, there is more than 92% probability that the toxicity rate of the maintenance therapy with lenalidomide is greater than 30%, the trial will be stopped. For the purpose of toxicity monitoring, toxicities are defined as any treatment-related clinically significant grade 3 or 4 non-hematologic AEs occurred any time during the trial, which are also outlined in Table 2. We will apply this stopping rule starting from the 10th patient and in cohort size of 10. The stopping boundaries corresponding to this toxicity monitoring rule are described in the following table:

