#### Stopping boundaries for treatment-related grade 3, 4 non-hematologic toxicities

The number of patients evaluated for toxicities	10	20	30	40	50
Stop the trial if greater than or equal to this many of patients with toxicities	6	10	13	17	20

The operating characteristics for toxicity monitoring are described in the following table. MultcLean Desktop 2.1.0 was used for the design and simulations for toxicity monitoring.

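### The trial-level toxicity rule pools all dose levels and was evaluated only for a single common rate, so it can have low power to detect excess toxicity confined to escalated patients

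*Combined protocol and SAP*

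**What the plan says.** Section 8.0 stops the trial if "there is more than 92% probability that the toxicity rate of the maintenance therapy with lenalidomide is greater than 30" percent. For this, "we assume a beta (0.6, 1.4) prior for" the toxicity rate, and the rule is applied "starting from the 10 th patient and in cohort size of 10". The event is one yes/no outcome per patient: "toxicities are defined as any treatment-related clinically significant grade 3 or 4 non-hematologic AEs occurred any time during the trial". The boundary table ("Stop the trial if greater than or equal to this many of patients with toxicities") gives 6/10, 10/20, 13/30, 17/40 and 20/50. The operating characteristics table lists early stopping probabilities at single true rates from 0.10 to 0.50. Section 9.1.1 makes every patient evaluable for toxicity from first treatment. None of this refers to dose.

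Dose is not constant. Under Section 4.1.1 all patients start at 10 mg daily. After cycle 1, those with minimal residual disease or morphologically active disease who tolerate the drug may move up: "A maximum of 2 dose escalations per patient are allowed if well tolerated". Table 1 lists 15 and 20 mg daily as the higher levels, and Section 6.1.1 adds that "Dose levels different than dose described may be allowed after discussion with the PI". Section 8.0 plans summaries by dose level for the correlative data but specifies none for toxicity.

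**The concern.** The monitored quantity is an average over patients who stay at or below the starting dose and patients who go above it. If toxicity is high only after escalation, the average can stay low enough that the rule seldom fires. The operating characteristics would not reveal this, because each of their scenarios gives every patient the same rate. The safety conclusion is also affected: a single final rate would describe a blend of doses and might match neither group. Assessing toxicity and safety is a stated secondary objective.

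Timing may add to the dilution. Escalation cannot begin before the end of cycle 1, while patients are evaluable from their first treatment, so some patients counted at early looks may not yet have received a higher dose.

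**Working it through.** **Inputs from Section 8.0.** Prior Beta(0.6, 1.4); limit 0.30; cut-off 0.92; looks at 10, 20, 30, 40 and 50 patients; maximum 50 patients.

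**Step 1: reproduce the plan's figures.** The boundary at n patients is the smallest r with Pr(Beta(0.6 + r, 1.4 + n − r) > 0.30) > 0.92. At n = 10, r = 5 gives 0.880 and r = 6 gives 0.963, so the boundary is 6. The same formula gives 10, 13, 17 and 20 at the later looks, matching the table. An exact binomial recursion over the looks at 10, 20, 30 and 40 (a crossing at 50 is not early) gives:

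| True rate | Recomputed early stop | Plan |
|---|---|---|
| 0.10 | 0.0002 | 0.0002 |
| 0.20 | 0.0101 | 0.010 |
| 0.30 | 0.1353 | 0.135 |
| 0.40 | 0.5419 | 0.542 |
| 0.50 | 0.9043 | 0.904 |

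**Step 2: mixed doses.** Let f be the share escalated, p_esc the toxicity rate in escalated patients and p_base the rate in the rest. The pooled rate is f × p_esc + (1 − f) × p_base, which goes through the same recursion. The protocol gives none of these three quantities; all values below are assumptions.

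| f | p_esc | p_base | Pooled rate | Early stop |
|---|---|---|---|---|
| 20% | 50% | 10% | 18% | 0.005 |
| 30% | 50% | 10% | 22% | 0.019 |
| 30% | 60% | 15% | 28.5% | 0.10 |
| 40% | 60% | 15% | 33% | 0.23 |
| 40% | 60% | 20% | 36% | 0.35 |
| 50% | 60% | 15% | 37.5% | 0.42 |
| 60% | 60% | 15% | 42% | 0.63 |

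For example, 0.30 × 0.50 + 0.70 × 0.10 = 0.22. Over f = 20-40%, p_esc = 50-60% and p_base = 10-20%, the range is 0.005 to 0.35. The pooled rate stays below 30% only if f < (0.30 − p_base)/(p_esc − p_base). With p_esc = 50%, that is f < 0.20/0.40 = 50% when p_base = 10%, and f < 0.10/0.30 = 33% when p_base = 20%.

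**Step 3: the same criterion on escalated patients only.** The Step 1 formula gives boundaries of 4 at 5, 6 at 10 and 8 at 15 escalated patients. The recursion then gives the flag probability:

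| True rate after escalation | Looks at 5 and 10 | Looks at 5, 10 and 15 |
|---|---|---|
| 30% | 0.06 | 0.08 |
| 50% | 0.41 | 0.56 |
| 60% | 0.66 | 0.82 |

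**Step 4: compare like with like.** The pooled early-stop figures leave out the look at full enrolment. At f = 30%, the 15th escalated patient is expected only at full enrolment (0.30 × 50 = 15), so the matching column is looks at 5 and 10. With p_esc = 50% and p_base = 10%, that is 0.41 against 0.019. At f = 20%, full enrolment yields about 10 escalated patients. Only the look at 5 is then early, and it flags with probability 0.19 at 50% and 0.34 at 60%; including the look at 10 gives 0.41 and 0.66.

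**The case against.** The pooled rate is a legitimate target: it describes the regimen as given, permitted titration included, and that is what Section 8.0 says it monitors. Patients also have individual protection. Escalation requires tolerating the starting dose, Table 2 in Section 6 calls for holding and reducing by one level after drug-related clinically significant grade 3-4 non-hematologic events, and serious events go to the drug supplier within 24 hours. All of this stands. But these measures respond to single patients; they do not accumulate evidence on whether escalation itself carries too much toxicity.

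A reader might infer that escalated patients will be a small minority, that their toxicity must be diluted below 30%, and that the rule would almost never react. The documents do not support this. Persistent minimal residual disease is one of the entry features for first-remission patients, and residual disease after cycle 1 is an escalation trigger, so the share could be large. Several mixtures above have pooled rates over 30% and stopping probabilities well above the plan's 0.135 at a uniform 30%.

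A reader might also infer that Section 2.4 contradicts Table 1. After citing chronic dosing at 10 mg in AML and 10-15 mg in myeloma, Section 2.4 says "These doses have therefore been shown to be safe and active in a long-term dosing strategy". That reports earlier experience and sets no ceiling; 15 mg lies inside the cited range. It cites no maintenance experience at 20 mg, which limits the rationale but is not an inconsistency.

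**Conclusion.** The point holds in a limited form. The only trial-level toxicity rule has no dose component, and its operating characteristics cover only a homogeneous rate. The rule itself is correctly computed. Its chance of stopping early when excess toxicity is confined to escalated patients is 0.005-0.35 over the main assumed grid and about 0.42-0.63 if 50-60% escalate with 60% against 15% toxicity. Where in that span the trial would fall cannot be settled from the protocol, because the escalated share and toxicity by dose are not given. The calculation also treats every patient as fully observed at each look, which favours the pooled rule if escalation and its toxicity come late.

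**What to change.** 1. Record the dose level at onset of every monitored toxicity.
2. When 5, 10 and 15 patients have been escalated, apply the existing criterion (Beta(0.6, 1.4), limit 0.30, cut-off 0.92) to toxicities with onset after escalation. The boundaries are 4/5, 6/10 and 8/15, used as a flag for safety review. Tie these looks to the number escalated, not to the pooled looks: at a 30% share those would fall at about 3, 6, 9, 12 and 15 escalated patients, where the same formula gives boundaries 3, 4, 5, 7 and 8 and a false-flag probability of 0.14 at a true 30%.
3. If more than 15 are escalated, extend the boundaries by the same formula.
4. Report the final toxicity rate separately for never-escalated and escalated patients.
5. Add at least one mixed-dose scenario to the operating characteristics table, stating the assumed share and rates.

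This needs no additional patients. It costs one data field, a short boundary table, slightly more monitoring work, and a false-flag chance of about 6-8% at a true 30% rate in escalated patients. Any dosing response to a flag is for the sponsor's clinical team to define.

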#### Stopping boundaries for treatment-related grade 3, 4 non-hematologic toxicities

The number of patients evaluated for toxicities	10	20	30	40	50
Stop the trial if greater than or equal to this many of patients with toxicities	6	10	13	17	20

The operating characteristics for toxicity monitoring are described in the following table. MultcLean Desktop 2.1.0 was used for the design and simulations for toxicity monitoring.

#### Operating characteristics for Toxicity Monitoring

True Toxicity Rate	Early Stopping Probability	Sample Size		
		25 th percentile	Median	75 th percentile
0.10	0.0002	50	50	50
0.20	0.010	50	50	50
0.30	0.135	50	50	50
0.40	0.542	20	40	50
0.50	0.904	10	20	30

The correlative biology studies are considered exploratory; trends and associations will be used to gain insight into the potential activity of this regimen and to help select potential biomarkers for further investigation in follow-up studies.

Correlative data will be reported by dose level with simple summary statistics: means (possibly after transformation) or medians, ranges, and standard deviations (if numbers and distribution

permit). Scatterplots will be used to explore possible associations between the dose and the immunomodulatory parameters, and between the immunomodulatory parameters and toxicity experienced (as reflected in the maximum grade of toxicity experienced or in clinical measurements). Scatterplots will also be used to explore possible associations between the immunomodulatory parameters, MRD, and relapse.

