## **9.0 MEASUREMENT OF EFFECT**

### **9.1 Criteria for Response**

#### **9.1.1 Definitions**

Evaluable for toxicity. All patients will be evaluable for toxicity from the time of their first treatment on study.

Evaluable for response. Patients who have received at least one cycle of therapy, and have had their disease re-evaluated will be considered evaluable for response. These patients will have their response classified according to the definitions stated below. (Note: Patients who exhibit objective disease progression prior to the end of cycle 1 will also be considered evaluable.)

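### The toxicity-monitoring table assumes every patient's toxicity status is final at each look; the written rule does not secure that, so its early-stopping figures are upper limits for stopping before full enrolment

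*Combined protocol and SAP*

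**What the plan says.** All of the trial-level toxicity monitoring is in section 8.0.

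- **Rule.** Stop if Pr(toxicity rate > 0.30 | data) > 0.92, with a beta(0.6, 1.4) prior.
- **What counts.** "toxicities are defined as any treatment-related clinically significant grade 3 or 4 non-hematologic AEs occurred any time during the trial". Sections 4.0 and 4.3 allow up to 24 months of drug.
- **When it is checked.** The section opens with "we will continuously monitor treatment-related toxicities using the Bayesian approach" and explains that the trial stops "if at any given time, there is more than 92% probability that the toxicity rate" exceeds 30%. It then applies the rule from the 10th "patient and in cohort size of 10".
- **Boundaries.** 6, 10, 13, 17 and 20 patients with toxicity at 10, 20, 30, 40 and 50. The row is labelled "The number of patients evaluated for toxicities"; how much follow-up makes a patient evaluated is not stated. Section 9.1.1 says only "All patients will be evaluable for toxicity from the time of their first treatment on study".
- **Operating characteristics.** The column headed "Early Stopping Probability" gives 0.0002, 0.010, 0.135, 0.542 and 0.904 at true rates 0.10 to 0.50. The sample-size quartiles are 20/40/50 at 0.40 and 10/20/30 at 0.50.
- **Accrual.** 1 patient per month expected; the RFS simulations used 2 per month. The toxicity table states no accrual or follow-up assumption.
- **Dose.** After cycle 1, in patients with persistent disease who tolerate the drug, "their dose may be increased to the next higher dose level for the remainder of the study", with at most two escalations.

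**The concern.** With a toxicity endpoint open for up to 24 months and a new patient every month, many patients at any look will still be at risk of a first qualifying event. They are in the denominator with no toxicity yet. Nothing in the rule makes the count at a look complete: there is no toxicity window, no minimum follow-up and no pause in accrual. Since escalation comes only after cycle 1, exposure that could cause toxicity also continues past the first weeks.

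At stake is how many patients enter before a toxic regimen is halted. This is the only trial-level toxicity rule, and the table is the only statement of what it delivers. A reader takes from it that a 50% toxicity rate would stop the trial before full enrolment nine times in ten, half the time by 20 patients. That holds only if toxicity status is final at each look.

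**Working it through.** **1. Boundaries.** Inputs are the prior, limit and cut-off in section 8.0. The boundary at n is the smallest x for which a beta(0.6 + x, 1.4 + n − x) variable exceeds 0.30 with probability above 0.92.

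| n | x | probability at x | at x − 1 |
|---|---|---|---|
| 10 | 6 | 0.962 | 0.880 |
| 20 | 10 | 0.961 | 0.906 |
| 30 | 13 | 0.929 | 0.863 |
| 40 | 17 | 0.946 | 0.900 |
| 50 | 20 | 0.926 | 0.876 |

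All five match the printed row.

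**2. The printed probabilities.** Exact sequential binomial calculation, every outcome known at each look, looks at 10, 20, 30 and 40:

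| True rate | Exact | Printed | Adding the 50-patient row |
|---|---|---|---|
| 0.10 | 0.0002 | 0.0002 | 0.0002 |
| 0.20 | 0.0101 | 0.010 | 0.0105 |
| 0.30 | 0.1353 | 0.135 | 0.160 |
| 0.40 | 0.5419 | 0.542 | 0.640 |
| 0.50 | 0.9043 | 0.904 | 0.957 |

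Cumulative stopping at the four looks is 0.166, 0.295, 0.470, 0.542 at 40% and 0.377, 0.630, 0.841, 0.904 at 50%. This gives the printed quartiles. A 25th percentile of 10 at the 50% rate requires ten final outcomes before the 11th patient enters. The table therefore means complete data, looks every 10 patients, stopping before full enrolment.

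**3. Direction.** Under those looks, an event not yet observed can only lower the count. The printed figures are upper limits whatever the onset pattern; no onset assumption is needed for this step.

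**4. Size.** Onset times are not in the documents, so they are assumed and shown as a range; none is ranked likelier. Simulation settings: 1 patient per month, evenly spaced; cycle = 28/30.44 month; onset in cycle 1, or uniform over 3 to 24 months, or uniform over time on drug (exponential with median 8 or 10.5 months, capped at 24). Chance of stopping before full enrolment at a 40% rate, against 0.542 printed:

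| Assumed onset | Look at nth start | One cycle later | 3 months later |
|---|---|---|---|
| Cycle 1 | 0.48 | 0.54 | 0.54 |
| Uniform, 3 months | 0.41 | 0.47 | 0.54 |
| Uniform, 6 months | 0.33 | 0.38 | 0.48 |
| Uniform, 12 months | 0.18 | 0.22 | 0.32 |
| Uniform, 24 months | 0.03 | 0.04 | 0.08 |
| Over time on drug | 0.18–0.22 | 0.23–0.27 | 0.31–0.35 |

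The cycle-1 start look can be checked exactly: status is known for n − 1 patients at the nth start, which gives 0.475.

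**5. What is lost.** At a 50% rate, complete-data mean enrolment is 10(0.377) + 20(0.253) + 30(0.211) + 40(0.063) + 50(0.096) = 22.5. With looks at the nth start it is 25.5 to 39.5 for onset within 12 months or over time on drug, and 47.7 for 24-month onset. Adding the 50-patient row, read 12 months after the last start, the rule triggers at some point in 0.92–0.95 of trials at 50% (0.87 for 24-month onset), against 0.957 with complete data. At 40% it triggers in 0.52–0.61 (0.40 for 24-month onset), against 0.640.

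**6. The continuous reading.** Checking after each patient from 10 to 49 with complete data gives 0.694 at 40% and 0.225 at 30%. The printed 0.542 and 0.135 do not describe that schedule.

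**The case against.** The strongest reply is that no printed number is wrong. Cohorts of 10, the boundary row and the operating characteristics agree with one another, and complete data is a common simplification. That stands: this is an unstated condition, and a reader who infers that the table is miscalculated goes beyond the evidence.

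It can also be said that cohorts of 10 is plainly the operative schedule and that continuous is loose wording. That is the better reading, since both tables fit only it. It settles the timing of looks but leaves follow-up undefined.

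A look at the nth patient's start is the harshest choice, and no section fixes it. With looks 3 months later and onset within 6 months, the range is 0.48–0.54, close to the printed value. Uniform 24-month onset also sits awkwardly with a planning median RFS of 8 to 10.5 months and 25% leaving for transplant. Both points limit the size of the shortfall; they do not change its direction.

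Two further inferences are tempting and unsupported. One is that late toxicities escape the rule: they count at later looks and at the 50-patient row, and step 5 shows detection at 50% largely intact. The other is that 0.542 caps all stopping under looks every 10 patients: with the 50-patient row the complete-data ceiling is 0.640.

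Patients are protected individually by dose holds and reductions (section 6, Table 2), removal for unacceptable toxicity (section 4.3) and SAE reports within 24 hours (section 10). None of these halts enrolment.

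**Conclusion.** The point holds in a limited form. The table is correct for complete data at looks of 10, 20, 30 and 40. The written rule does not secure complete data, so 0.542 and 0.904 are ceilings for stopping before full enrolment.

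That conclusion rests on the documents alone; the size of the shortfall does not. At 40% and 1 patient per month it is nil to 0.07 if onset is in cycle 1, and larger if onset is spread over 6 to 12 months or more (0.33 and 0.18 with start looks). The documents do not support calling any one of these the expected figure. The main consequence is later stopping and more patients enrolled. The mismatch between continuous wording and cohorts of 10 is secondary but should be resolved, because the two schedules have different operating characteristics.

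**What to change.** 1. Label the present table *complete data, looks every 10 patients, stopping before full enrolment*. Add operating characteristics at 1 patient per month under stated early- and late-onset assumptions.

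2. To match the any-time wording, replace the cohort schedule with: *The rule is checked when the 10th patient starts treatment and at every new qualifying toxicity after that, until the last patient is off drug. A patient counts as evaluated from the first dose.* Keep the prior, the 30% limit, the 0.92 cut-off and the toxicity definition. Print the boundary for each n: 6 at 10–11, 7 at 12–14, 8 at 15–16, 9 at 17–19, 10 at 20–22, 11 at 23–24, 12 at 25–27, 13 at 28–30, 14 at 31–33, 15 at 34–36, 16 at 37–38, 17 at 39–41, 18 at 42–44, 19 at 45–47, 20 at 48–50.

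Effect on stopping before full enrolment, looks at the nth start against the fix:

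| Onset | 40% rate | 30% rate |
|---|---|---|
| Cycle 1 | 0.48 → 0.69 | 0.10 → 0.23 |
| Uniform, 12 months | 0.18 → 0.39 | 0.02 → 0.06 |
| Uniform, 24 months | 0.03 → 0.12 | 0.001 → 0.008 |

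The plan should state both limits: stopping at exactly the 30% limit rises, and late-onset stopping at 40% stays below 0.542. The cost is two sentences, a longer boundary table and one new simulation, with no extra patients or visits; at a single centre each check is a table look-up. Counting a patient as evaluated only at the first toxicity or after three cycles, or moving the cut-off to 0.95, are optional trade-offs and not needed for this correction.
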